2 BACKGROUND AND RATIONALE

2.1 Background information on Recurrent Urinary Tract Infection (rUTI)

Urinary tract infection (UTI) is a very common outpatient diagnosis among healthy young women, resulting in considerable morbidity and health care costs. In 1997, UTI accounted for approximately 11 million doctor visits. Approximately 33% of these women experience two or more UTIs per year. A recent population survey of women in the United States found that the lifetime risk of UTI was over 60% and that the estimated societal cost of UTIs exceeds 25 billion dollars over 20 years (1). To date, the only effective method of reducing the high risk of UTI in pre-menopausal women with a history of recurrent urinary tract infection (RUTI) is antimicrobial prophylaxis, a strategy that is becoming less effective as antimicrobial resistance amongst uropathogens increases (2). In addition, antibiotic resistance, even among community-acquired UTIs, is making treatment of these infections more problematic (3).

Thus, novel, safe and effective non-antimicrobial prevention strategies are urgently needed. One such approach, for which there is strong evidence at the mechanistic level, is use of an H₂O₂-producing *Lactobacillus* to restore the normal vaginal microbiota (4). If effective in reducing *E. coli* colonization and UTI, this strategy would reduce the costs and morbidity associated with urinary tract infections, including time lost from work, health care costs, antimicrobial use, and the ultimate development of antimicrobial resistance.

Many studies have confirmed that the critical event preceding a UTI is colonization of the vaginal introitus with gut microbiota, most commonly *E. coli* (5, 6). Women with recurrent UTI are more likely to be vaginally colonized with *E. coli* or other *Enterobacteriaceae* than women without recurrent UTI, and demonstrate prolonged periods of persistent colonization. Recent studies have verified these findings and have demonstrated a coincident loss of the normally predominant vaginal lactobacilli [10, 11, 12]. In a study in women of reproductive age, 15% of 302 women who had vaginal colonization with *L. crispatus* or *L. jensenii*, both H₂O₂ producers, were colonized with *E. coli* as compared with 27% of women who did not have these lactobacilli species present ($p = 0.01$) (7). This and other data suggest that H₂O₂-producing lactobacilli may have an important role in the maintenance of the normal vaginal ecology and in the prevention of vaginal colonization with *E. coli* and thus *E. coli*-induced UTI.

Mechanistic studies also support the ability of H₂O₂-producing lactobacilli to exclude *E. coli* vaginal colonization. Thus, Osset and colleagues showed that such lactobacilli are capable of competitive exclusion, blocking adherence of *E. coli* to vaginal epithelial cells (8). In addition, *L. crispatus* inhibits the growth of *E. coli* in both liquid and solid media through the action of H₂O₂. Finally, recent studies at the University of Washington have

shown that *L. crispatus* adheres extremely well to vaginal epithelial cells from women with recurrent UTI, suggesting it will colonize such women's vaginal epithelium (9).

2.2 History of product development

2.2.1 Pre-clinical research

In 1987, research conducted by Giorgi et al. suggested that the most common *Lactobacillus* in the human vagina is not *Lactobacillus acidophilus*, but rather *Lactobacillus crispatus*, *Lactobacillus jensenii* and *Lactobacillus gasseri* (10). Additional studies performed in the laboratories of [name] at the University of Pittsburgh confirmed that *Lactobacillus crispatus* is the predominant H₂O₂-producing *Lactobacillus* found in the vagina of a healthy woman (7).

LACTIN-V, the product under investigation in this Phase 3 study, contains *Lactobacillus crispatus* CTV-05 bacteria preserved by spray drying with a simple drying medium. The product is prepared as a powder in an applicator for intravaginal use. *Lactobacillus crispatus* is a naturally occurring organism isolated from the vagina of a healthy woman in 1993. Using repetitive sequence polymerase chain reaction (rep-PCR) DNA fingerprinting, investigators distinguished *L. crispatus* CTV-05 from other *Lactobacillus* strains derived from the human vagina. Additionally, it was demonstrated that this strain produces high levels of lactic acid and H₂O₂ (11).

Osel, Inc. plans to develop LACTIN-V for the following indications:

1. To reduce the recurrence rate of urinary tract infection in women with recurrent uncomplicated UTI (RUTI), including acute, uncomplicated cystitis and pyelonephritis.
2. To reduce the recurrence rate of bacterial vaginosis (BV) in women with recurrent BV.

2.2.2 Clinical research

2.2.2.1 Lactin-Vaginal

The first product containing *L. crispatus* CTV-05, Lactin-Vaginal, was under development by The Medicines Company and subject to an IND sponsored by the NIH (BB-IND 6603). In previous clinical studies (three non-IND and two IND) conducted between 1991 and 2000, a total of 304 women received Lactin-Vaginal and were considered evaluable. Although the overall results of the Phase II/III study with Lactin-Vaginal indicated no significant improvement in the cure rate for BV when Lactin-Vaginal was administered with a single 2 gram dose of metronidazole, the

subset of subjects who received Lactin-Vaginal and were colonized with *Lactobacillus crispatus* CTV-05 had a significantly higher clinical cure rate at 30 days than those who were not colonized.

In this Phase II/III study, Lactin-Vaginal was shown to be safe. Adverse events that were reported in the phase II/III study of Lactin-Vaginal (Protocol No. 99-033) were equally distributed between the Lactin-Vaginal and placebo control substance groups, and thus were unlikely related to the *L. crispatus* CTV-05, with the exception of increased vaginal discharge while using the capsules. All 355 women received a single 2 gram oral dose of metronidazole and then were randomized to either Lactin-Vaginal or a control vaginal capsule. Adverse events reported in at least 10% of subjects in this study were abdominal pain, nausea, upper respiratory infections, urinary tract infections, bacterial vaginitis, yeast vaginitis, back pain, urinary frequency, genital pruritus, intermenstrual bleeding, menorrhagia and vaginal discharge. Other less commonly occurring AEs reported included dysuria, urinary urgency, nocturia, dysmenorrhea, vaginal burning and/or pain, genital burning, genital erythema, genital edema, genital lesions, vaginal odor, diarrhea, constipation, dyspareunia, and skin rash. The following Serious Adverse Events were reported in subjects who received Lactin-Vaginal, but all were considered unrelated to treatment: a spontaneous abortion which occurred 69 days after randomization; a ruptured ectopic pregnancy which occurred 79 days after randomization; and a gall bladder removal 92 days after randomization.

Osel, Inc. has acquired the commercialization rights for this product and also the manufacturing facilities used to produce Lactin-Vaginal. Osel, Inc. planned to develop the product for the following indications:

1. To reduce the recurrence rate of BV.
2. To reduce the recurrence rate of urinary tract infections in women with recurrent uncomplicated UTI (RUTI)

2.2.2.2 LACTIN-V

Two rounds of important modifications have been made to the original Lactin-Vaginal product by The Medicines Company. The new product developed by Osel, Inc. was called LACTIN-V.

The first formulation of LACTIN-V (Formulation 1) incorporated the following changes into the manufacturing process and was used in the trials LV 001 – LV004:

- Preparation of a new Master Cell Bank;
- Reformulation to reduce the quantity of fermentable sugars in the final study product; this reformulation has resulted in a more potent study product;

- Replacement of the fermentation medium with an animal by-product-free medium;
- Changes in the fermentation process leading to the harvest of bacteria in a “log growth phase” versus “stationary growth phase”;
- Increase in the number of viable bacteria per capsule;
- Reduction in the size of gelatin capsules
- Reduction in the volume of the capsule

LACTIN-V (Formulation 1) contains *Lactobacillus crispatus* CTV-05 bacteria preserved as a dry powder. Using repetitive sequence polymerase chain reaction (rep-PCR) DNA fingerprinting, investigators distinguished *L. crispatus* CTV-05 from other *Lactobacillus* strains derived from the human vagina. Additionally, it was demonstrated that this strain produces high levels of lactic acid and H₂O₂ (11).

LACTIN-V (Formulation 1) has been tested in several phase I and phase II studies:

LACTIN-V Study LV-001

Osel, Inc. completed an initial Phase I study of LACTIN-V (Formulation 1) in healthy pre-menopausal women (Study No. LV-001) under BB-IND 11363. In LV-001, 60 women were randomized (1:1:1:1) between four groups: low dose LACTIN-V at 5 x 10⁶ cfu/capsule; high dose LACTIN-V at 5 x 10⁸ cfu/capsule; control capsule; and untreated. Commencing at Visit 1 (Day 1), all capsule recipients inserted one capsule daily for five consecutive days and returned to the clinic for two follow-up visits (Visit 2 between Days 6–8 and Visit 3 between Days 26–34). Safety was evaluated by symptoms, pelvic examinations, colposcopy and urinalyses. Colonization and shifts in other vaginal microbiota were assessed at Day 7 (+/-1) and at Day 30 (+/-4). Colonization data indicates that approximately twice as many subjects in the LACTIN-V 5 x 10⁸ cfu/capsule dose arm (approximately 40% colonization rate) versus the LACTIN-V 5 x 10⁶ cfu/capsule dose cohort (approximately 20% colonization rate) were successfully colonized with *L. crispatus* strain CTV-05 at Day 30.

No serious adverse events were reported in Protocol No. LV-001, and no subject left the protocol due to an adverse event. Long-term safety was assessed by a telephone follow-up at Month 6. Most AEs were mild to moderate. No single severe AE was experienced by more than one subject. Three subjects each experienced a single severe, treatment-related AE: abdominal pain, vaginal candidiasis, vaginal burning sensation, vaginal hemorrhage and vaginal irritation. There were no notable, unexpected AEs, no SAEs and no deaths. No subject left the study due to an AE. The most frequent (≥10%) non-gynecologic AEs reported regardless of causality were abdominal pain NOS (25.0%), headache NOS (23.3%) and diarrhea NOS (10.0%). The most frequent (≥10%) gynecologic AEs reported were vaginal discharge (35.0%), genital pruritis female

(26.7%), vaginal hemorrhage and vaginal odor (15.0%, each), and vaginal burning sensation and vaginal candidiasis (11.7%, each). Forty (88.9%) of subjects participating in this study experienced an AE that was considered by the Investigator to be possibly or probably related to study treatment (LACTIN-V or control capsule). The most common ($\geq 10\%$) non-gynecologic AEs reported as possibly or probably related to study treatment were abdominal pain NOS (22.2%), headache NOS (17.8%) and diarrhea NOS and vaginal candidiasis (11.1%, each). The most common ($\geq 10\%$) gynecologic AEs that were reported by the Investigator as possibly or probably related to study treatment were vaginal discharge (46.7%), genital pruritis female (31.1%), vaginal odour (20.0%), vaginal hemorrhage (17.8%) and vaginal burning sensation (15.6%).

Results obtained indicate that LACTIN-V is safe and well tolerated when administered to healthy subjects once a day for five days at either 5×10^6 cfu/capsule or 5×10^8 cfu/capsule. The safety and vaginal microbiota changes in the placebo control group demonstrated that it was a valid comparison group for use in future studies, instead of using an untreated group.

LACTIN-V Study LV-002

Osel, Inc. conducted a second Phase I study, Protocol No. LV-002, in a cohort of healthy pre-menopausal women with a history of uncomplicated recurrent UTI. The design of this study was similar to Protocol No. LV-001 with the exception that there were 30 women randomized (1:1) to receive either LACTIN-V Formulation 1 (5×10^8 cfu/capsule) or the control capsule once daily for five days. Safety was evaluated by symptoms, urinalyses and pelvic examination. Colonization was assessed at Day 7 (+/- 1) and at Day 30 (+/-4), in addition to shifts in other vaginal microbiota. Long-term safety was assessed by a telephone follow-up at Month 6. In general, the study product was well tolerated.

A high rate of positive *L. crispatus* strain CTV-05 assays at study baseline in the Evaluable Cohort (33.3% and 7.7% in the LACTIN-V and the control capsule groups, respectively) may have been due to a lack of specificity of the assay. The CTV-05 rep-PCR assay, which was still under development at the time, may have lacked sufficient specificity in this study to distinguish between endogenous, H_2O_2 -producing *L. crispatus* and the CTV-05 (LACTIN-V) strain of *L. crispatus*. The CTV-05 colonization rates observed in subjects receiving LACTIN-V in this study (40.0% at Visit 2 and Visit 3) were lower than anticipated, possibly due to the high rate of endogenous lactobacilli at baseline in this population of healthy pre-menopausal women. All study subjects in the Evaluable Cohort were vaginally colonized with H_2O_2 -producing lactobacilli at study entry, and they remained colonized throughout the study. It was anticipated that in women with disrupted vaginal microbiota and reduced lactobacilli following antibiotic treatment of recurrent BV or RUTI, the CTV-05 colonization rates would be higher.

In Protocol No. LV-002, LACTIN-V appeared to be safe and well tolerated when administered intravaginally for five consecutive days at a dose of 5×10^8 cfu/capsule.

All AEs were mild to moderate; no severe or severe, related AEs were reported. There were no notable, unexpected AEs, no SAEs and no deaths. No subject left the study due to an AE. Fourteen subjects in the LACTIN-V group reported a total of 37 events. In the control group, 14 subjects reported a total of 41 events. Overall, the most frequent ($\geq 10\%$) non-gynecologic AEs reported regardless of causality were headache NOS (43.3%), abdominal pain NOS (23.3%) and back pain (13.3%). The most frequent ($\geq 10\%$) gynecologic AEs reported were vaginal discharge (43.3%), female genital pruritis (13.3%), vaginal candidiasis (13.3%) and dysmenorrhea (10.0%). Twenty-two (73.3%) of the 30 subjects participating in this study experienced an AE that was considered by the Investigator to be possibly or probably related to study treatment (10 subjects in the LACTIN-V group, 12 subjects in the control group). The most common ($\geq 10\%$) AEs that were reported by the Investigator as possibly or probably related to study treatment were vaginal discharge (43.3%), female genital pruritis (13.3%) and vaginal candidiasis (13.3%). Six subjects in the LACTIN-V group reported a total of six events that were considered to be possibly related to study treatment, five subjects reported six events that were probably related, and one subject reported an event that was considered by the Investigator to be related to study treatment (mild vaginal discharge). In the control group, eight subjects reported a total of eleven events that were considered to be possibly related to study drug, six subjects reported six events that were probably related, and one subject reported an event that was considered to be related to study treatment (moderate vaginal discharge). None of the AEs reported were considered to be severe. Five subjects in the LACTIN-V group reported eight events that were considered to be moderate. All of these events were considered unrelated to study treatment, with the exception of a single occurrence of vaginal candidiasis, which was considered to be possibly related. Five subjects in the control group reported a total of eight moderate AEs. Long-term safety was assessed by a telephone follow-up at Month 6. The study was published in 2007 (12).

LACTIN-V Study LV-003

In 2005-2006, Osel Inc. conducted a Phase II, randomized, double-blind, placebo-controlled, multi-center study to assess safety, colonization rate and efficacy of preventing recurrence of bacterial vaginosis (BV). The study was conducted in 149 women with a history of recurrent BV who had recently been treated with a course of intravaginal metronidazole or clindamycin. Following completion of the prescribed course of antibiotic, each subject was randomized (1:1) at Visit 2 (Day 1) to receive either one LACTIN-V (Formulation 1) capsule at a dose of 5×10^8 colony forming units (cfu) per capsule daily for five days followed by one capsule per week for 10 weeks or the placebo capsule on the same schedule. Of those subjects who had *Lactobacillus* culture results, the percentage of subjects who were colonized with the *L. crispatus*, CTV-05 strain was significantly greater in the LACTIN-V group compared to the placebo group for both the modified intent-to-treat (MITT) and according-to-

protocol (ATP) cohorts [41.7% vs. 6.2%, respectively, in the MITT cohort ($p=0.0000$) and 59.3% vs. 12.1%, respectively, in the ATP cohort ($p=0.0023$)]. Although not reaching levels of statistical significance, the rate and the incidence of reported symptomatic BV episodes was lower in the LACTIN-V group compared to the placebo group (in both the MITT and ATP cohorts). In addition, the time to first recurrence of symptomatic BV was longer in LACTIN-V subjects compared to placebo subjects in the MITT cohort (118.7 days) in the LACTIN-V group and 98.7 days in the placebo group. Although overall encouraging, the provided data could not fully answer the research question of efficacy of prevention of BV recurrence due to low sample size and a low colonization rate of 41.7% for the MITT cohort and 59.3% for the ATP cohort.

For Protocol No. LV-003, 111 of 149 subjects (74.5%) reported at least one AE (76.7% of LACTIN-V subjects and 72.4% of placebo control substance subjects). Overall, the most common AEs reported were vaginal discharge (38.9%), vaginitis bacterial NOS (24.2%), genital pruritis female (23.5%) and vaginal odour (22.1%). Adverse events were mostly mild (67.8%) or moderate (28.2%) in severity, and the majority of subjects had AEs that were assessed as possibly or probably related to study product (56.4%). No safety signal was observed for the LACTIN-V group in regard to AEs, with the exception of a higher rate ($\geq 5\%$ difference between treatment groups) of nausea, diarrhea, dysuria, vaginal discharge and vaginal odour. One subject experienced three simultaneous SAEs (hemiparesis, blurred vision in right eye and headache); however, as this subject was in the placebo control substance group, the SAEs were unrelated to LACTIN-V. Two subjects in the LACTIN-V group discontinued study treatment due to AEs; one subject became pregnant and the other reported nausea and diarrhea, which required treatment. No deaths were reported during this study.

LACTIN-V study LV-004

A conducted by Osel Inc. was planned to involve 100 women with a history of recurrent, uncomplicated UTIs who had recently been treated for UTI with a course of antibiotics. Only subjects treated with amoxicillin/clavulanate (Augmentin), a quinolone or nitrofurantoin would have been eligible for enrollment. Subjects were to be randomized to one of two groups (50 subjects per group) to either receive one capsule of LACTIN-V Formulation 1 (at 5×10^8 cfu/capsule) or one placebo daily for five days followed by one capsule per week for 10 weeks. In addition to safety, this study was to evaluate the preliminary efficacy of LACTIN-V in reducing the incidence of symptomatic, probable and asymptomatic UTI. Subjects were to be queried at each clinic visit for urinary symptoms, including dysuria, frequency, urgency, hematuria, flank pain or suprapubic pain. This study was to also evaluate vaginal colonization with lactobacilli, *Lactobacillus crispatus*, strain CTV-05 and *E. coli* following administration of LACTIN-V.

The trial was halted due to logistical difficulties after only four subjects had been enrolled at three of the six study sites. Due to an enrollment rate that was much slower than expected, even after the addition of two more study sites, Study No. LV-004 was closed to further recruitment much in advance of reaching the target enrollment number of 100. Among the four subjects that completed the study and were being followed for long-term safety, a total of six AEs were reported during the study in two subjects in the LACTIN-V group. All of the AEs were considered by the Investigator to be of moderate severity and unrelated to study treatment. There were no severe or severe related AEs. There were no notable, unexpected adverse events, no serious adverse events and no deaths.

LACTIN V study UW/LB-001

Following the problems with low enrollment described above for LV-004, a study with similar study design using LACTIN-V for prevention of recurrent UTI was undertaken at the University of Washington. In addition to safety, this study was to evaluate the preliminary efficacy of LACTIN-V in reducing the incidence of symptomatic, probable and asymptomatic UTI. In the study UW/LB-001, 100 young healthy women with a history of recurrent UTI received antimicrobials for acute UTI and then were randomized to one of two groups (50 subjects per group) to either receive one capsule of LACTIN-V Formulation 1 (at 5×10^8 cfu/capsule) or one placebo daily for five days followed by one capsule per week for 10 weeks. Participants were followed up at 1 week and 10 weeks after intervention and for UTIs; urine samples for culture and vaginal swabs for real-time quantitative 16S ribosomal RNA gene polymerase chain reaction for *L. crispatus* were collected. This study was to also evaluate vaginal colonization with lactobacilli, *Lactobacillus crispatus*, and strain CTV-05 following administration of LACTIN-V.

Recurrent UTI occurred in 15% (7/48) of women receiving Lactin-V compared with 27% (13/48) of women receiving placebo (relative risk [RR], .5; 95% confidence interval, .2–1.2). High-level vaginal colonization with *L. crispatus* ($>10^6$ 16S RNA gene copies per swab) throughout follow-up was associated with a significant reduction in recurrent UTI only for Lactin-V (RR for Lactin-V, .07; RR for placebo, 1.1; $P < .01$).

Adverse effects were reported by 56% of participants who received Lactin-V and by 50% of participants who received placebo; the most common adverse effects included vaginal discharge or itching or moderate abdominal discomfort. One participant in the placebo group discontinued treatment because of adverse effects. The incidence of BV or candidal vaginitis was low in both treatment groups (0%–5%), and there was no significant difference in rates of pyuria between the 2 groups (rate at visit 3 among women in the Lactin-V group, 13%; rate at visit 3 among women in the placebo group, 22%; rate at visit 4 among women in the Lactin-V group, 32%; rate at visit 4 among women in the placebo group, 33%). No serious AEs or episodes of pyelonephritis were reported in either group. This study was published in 2011 and concluded that Lactin-V after treatment for cystitis is associated with a reduction in recurrent UTI (13).

LACTIN-V study LV-005

As a result of the non-optimal colonization rate using LACTIN-V (Formulation 1) delivered in capsules, as seen in Protocols No. LV-003 and LV-004, it was recognized that the gelatin capsule used in the previous LACTIN-V dosage form dissolved slowly in the vagina, likely contributing to sub-optimal colonization of the bacteria. To circumvent this problem and improve the colonization rates of *L. crispatus* CTV-05, a new round of study product and protocol improvements incorporated the following measures:

- Elimination of the gelatin capsule
- Development of a pre-filled vaginal applicator for administration of the LACTIN-V powder formulation directly into the vagina without a capsule (Formulation 1 in applicator)
- Increasing the amount of *L. crispatus* CTV-05 per dose (i.e., per applicator) from 5×10^8 (150 mg) to 2×10^9 cfu/dose (600 mg)
- Elimination of the lag time between completion of antibiotic treatment and initiation of LACTIN-V dosing

In late 2007 Osel commenced a small phase I dose-ranging clinical study (LV-005) to assess the safety, tolerability and acceptability of LACTIN -V (Formulation 1) powder delivered with pre-filled vaginal applicators in healthy pre-menopausal women. Study Protocol No. LV-005 also assessed higher doses than used in the prior LV-001 to LV-004 studies; increasing the amount of *L. crispatus* CTV-05 per dose (i.e., per applicator) from 5×10^8 (150 mg) to 1×10^9 (300 mg) and 2×10^9 cfu/dose (600mg). Twelve healthy volunteers were enrolled in 3 blocks of 4 (5×10^8 , 1×10^9 , and 2×10^9 cfu/dose). Each block was randomized in a 3:1 ratio of active product to placebo. Participants used study product for 5 consecutive days, returned for follow-up on days 7 and 14, and had phone interviews on days 2 and 35.

All 12 subjects took 5 doses and completed study follow-up. No SAEs were reported for Study Protocol No. LV-005. All 12 participants took 5 doses and completed study follow-up. Overall, 45 adverse events (AEs) occurred, of which 31 (69%) were genitourinary (GU) AEs. GU AEs appeared evenly distributed between the 3 treatment blocks and between LACTIN-V and placebo arms. The most common GU AEs were vaginal discharge in 5 subjects (42%), abdominal pain in 4 subjects (33%), metrorrhagia in 4 subjects (33%), vulvovaginitis in 4 subjects (33%), vaginal candidiasis in 3 subjects (25%), and vaginal odor in 3 subjects (25%). Forty-one (91%) AEs were mild (grade 1) in severity. All 4 moderate AEs (grade 2) were unrelated to product use. No grade 3 or 4 AEs or serious adverse events (SAE) occurred. Laboratory parameters and colposcopy findings were within normal limits or clinically insignificant. The product was well tolerated and accepted. The study concluded that all 3 dosage levels of LACTIN-V appeared to be safe and acceptable in healthy volunteers. This study was published in 2009 (14).

LACTIN-V study LV-006

Following the phase I clinical study LV-005, Osel, Inc. completed a phase IIa clinical study to further assess the colonization efficiency of *L. crispatus* CTV-05 in otherwise healthy pre-menopausal women diagnosed with BV, administered immediately after completion of a standard antibiotic treatment with metronidazole (MetroGel), using the pre-filled vaginal applicator. In addition, safety, tolerability and acceptability of LACTIN-V (Formulation 1) were assessed.

In this Phase IIa study, twenty-four women with BV were randomized in a 3:1 ratio of active product to placebo. Participants used LACTIN-V at 2×10^9 colony-forming units (cfu)/dose or placebo for 5 initial consecutive days, followed by a weekly application over 2 weeks. They returned for follow-up on Days 10 and 28. Sixty-one percent of the 18 women randomized to the LACTIN-V group were colonized with *L. crispatus* CTV-05 at Day 10 or Day 28. Among LACTIN-V users with complete adherence to the study regimen, 78% were colonized at Day 10 or Day 28. Of the 120 adverse events (AEs) that occurred, 108 (90%) and 12 (10%) were of mild and moderate severity, respectively. AEs were evenly distributed between the LACTIN-V and placebo group. Of the total AEs, 93 (78%) were genitourinary in origin. The most common genitourinary AEs included vaginal discharge (46%), abdominal pain (46%), dysuria (21%), pollakiuria (21%), vaginal odor (21%), and genital pruritus (17%). No grade 3 or 4 AEs or serious AEs occurred and no deep epithelial disruption was seen during colposcopic evaluation. The product was well tolerated and accepted. The applicator and dosage modifications resulted in a more potent LACTIN-V product (Formulation 1 in applicator) and an improved clinical protocol, leading to higher colonization and thus greater efficacy to prevent recurrent BV (15).

In early clinical studies conducted by The Medicines Company between 1991 and 2000, a total of 304 women received Lactin-Vaginal and were considered evaluable.

Although the overall results of the phase II/III study with Lactin-Vaginal indicated no significant improvement in the cure rate for BV when the study product was administered with a single 2 gram dose of metronidazole, the subset of subjects colonized with *L. crispatus* CTV-05 had a better clinical outcome. In this study, Lactin-Vaginal was demonstrated to be safe, with no category of adverse events occurring at a statistically higher frequency in the Lactin-Vaginal group than among controls. Later studies conducted by Osel, Inc. with the product LACTIN-V (Formulation 1 in capsule) at 5×10^6 or 5×10^8 cfu/capsule (Protocol No. LV-001 through LV-004) included more than 200 women (half of them being exposed to LACTIN-V) and provided excellent data on the safety of the study product.

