10.10.7 Assessment of Protocol Compliance

Every attempt will be made to select subjects who are eligible and will comply with the protocol. Noncompliant subjects may be discontinued from the study. Protocol deviations will be listed and summarized by treatment arm.

11 RISKS AND DISCOMFORTS TO STUDY SUBJECTS**11.1 LACTIN-V and Placebo Applicator Users****11.1.1 Risks**

The potential risks of LACTIN-V are currently unknown. Pelvic examinations and analyses of vaginal discharge and vaginal microbiota were included in the Phase 1 studies designed to assess LACTIN-V's safety and colonization. The initial Phase 1 safety study of LACTIN-V in healthy women, Protocol LV-001, included colposcopy to evaluate for inflammation or other lesions of the vaginal, cervical or vulvar epithelium. There were no significant differences noted in these safety parameters between treated subjects and those who remained untreated or received the placebo capsule (Osel, Inc., personal communication).

Risks from the administration of LACTIN-V are low since colonization with this type of organism is strongly associated with improved vaginal health. No systemic risks are anticipated, since this is an organism that is applied topically, and thus not absorbed. These risks will be explained in the written informed consent form. Pregnant women, fetuses, prisoners, children, persons with or at risk of STD or women undergoing in vitro fertilization will not be included in this study.

Potential risks to subjects participating in this study include genital or vaginal irritation or symptoms. In the initial Phase 1 study of LACTIN-V (LV-001), the following adverse events were experienced in (at least two) more LACTIN-V treated subjects when the treated groups were compared to the placebo and untreated groups: vaginal discharge, abdominal pain, genital pruritis, vaginal odor, vaginal burning sensation, vaginal candidiasis and diarrhea (Osel, Inc., personal communication). There is also the risk of an allergic reaction to the latex in the condoms provided to subjects who are unaware of their latex allergy and who use these condoms.

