11.1.2 Benefits

Research subjects, whether they receive LACTIN-V or placebo, will have the benefit of an office visit and urine culture, often omitted for this condition. Subjects will also have the benefit of having a pap smear. In addition, subjects participating in this clinical trial may contribute to the body of knowledge in the field of preventing recurrent urinary tract infections.

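### Section 11 omits nausea and dysuria, both reported more often on LACTIN-V than placebo in LV-003, and promises a Pap smear that no study visit includes

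*Combined protocol and SAP*

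**What the plan says.** **Risks (11.1.1).** The section opens with "The potential risks of LACTIN-V are currently unknown". It then calls the risks low and adds "These risks will be explained in the written informed consent form". It gives a general statement, "Potential risks to subjects participating in this study include genital or vaginal irritation or symptoms", and one study-specific list. That list is introduced by "In the initial Phase 1 study of LACTIN-V (LV-001), the following adverse events were experienced in (at least two) more LACTIN-V treated subjects" and reads "vaginal discharge, abdominal pain, genital pruritis, vaginal odor, vaginal burning sensation, vaginal candidiasis and diarrhea". No other LACTIN-V study is drawn on for named events.

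**The record (2.2.2.2, LV-003).** The background reports no safety signal for LACTIN-V, but makes an exception for a rate at least 5% higher than on placebo "of nausea, diarrhea, dysuria, vaginal discharge and vaginal odour". It also reports that one woman on LACTIN-V stopped treatment because of nausea and diarrhea.

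**Benefits (11.1.2 and 11.1.4).** Section 11.1.2 states "Subjects will also have the benefit of having a pap smear". Section 11.1.4 lists the Pap smear again when it weighs benefits against risks.

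**The concern.** Section 11 is the protocol's own summary of what a participant stands to gain and lose, and it points to the consent form. A statement that risks are unknown does not fit a document that describes several completed LACTIN-V studies and lists excess events in one of them. The study left out is the larger and longer one: LV-003 had 149 women and five daily then ten weekly capsules, against 60 women and five daily capsules in LV-001. LV-003 is also closer to the daily-then-weekly pattern used here.

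Dysuria deserves a line of its own. It is one of the symptoms that define both Symptomatic and Probable UTI (3.3.1, 3.3.2), so a woman joining a UTI-prevention trial has a particular interest in knowing it was reported more often on the product.

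The Pap smear is a plain mismatch: a screening test is offered as a benefit but is not among the study procedures.

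**Working it through.** This is a check of text against text. The plan gives no figure to reproduce beyond the LV-003 percentages.

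**Step 1. Compare the event lists.** Inputs: the five LV-003 terms (2.2.2.2) and the seven terms in 11.1.1.

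| LV-003 term, higher on LACTIN-V | Named in 11.1.1 |
|---|---|
| Nausea | No |
| Diarrhea | Yes |
| Dysuria | No |
| Vaginal discharge | Yes |
| Vaginal odour | Yes |

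Three of five are covered and two are missing. The general phrase about genital or vaginal symptoms does not cover nausea and does not name dysuria. Neither word occurs anywhere else in section 11.

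**Step 2. What the LV-003 figures allow.** The overall adverse event percentages are consistent: 111/149 = 74.5%. Among splits with 60 to 89 women on LACTIN-V, the stated 76.7% and 72.4% fit only 56/73 and 55/76 (56 + 55 = 111; 73 + 76 = 149). Counts by arm for nausea and dysuria are not given, so the differences themselves cannot be reproduced. I read the 5% as percentage points. Taking 73 against 76 and assuming placebo counts from 0 to 15, the smallest difference that qualifies gives:

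- 4/73 (5.5%) against 0/76 (0.0%): two-sided Fisher p = 0.055
- 19/73 (26.0%) against 15/76 (19.7%): two-sided Fisher p = 0.44

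A difference that only just meets the threshold is therefore compatible with chance. The actual differences may be larger.

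**Step 3. What the applicator studies add.** LV-005 randomized 12 women 3:1, so 9 active and 3 placebo. LV-006 randomized 24, with 18 active and so 6 placebo. Together that is 27 against 9, and one placebo woman is 1/9 = 11.1%. LV-006 describes adverse events as evenly distributed. LV-005 says so for genitourinary events, which does not bear on nausea. These studies are context, but they are too small to show or exclude a 5-point difference.

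**Step 4. Look for the Pap smear.**

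| Place | Pap smear or cervical cytology |
|---|---|
| Visit 0 (6.3.3) | None |
| Visit 1 (6.3.4) | None; cervix inspected by eye; swabs for pH and wet mount, Gram stain, culture and rep-PCR, stored DNA |
| Visits 2 to 5 (6.3.5) | None |
| Unscheduled visits (6.3.6) | None |
| Laboratory procedures (6.9.1, 6.9.2) | None |
| Flow chart, Visits 0 to 6 | None in any of seven columns |

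Visit 6 has no procedure list in the text, but its flow-chart column shows a pelvic examination and no smear. Outside section 11 the term appears only in the list of abbreviations.

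**The case against.** The strongest reply is that section 11 is less bare than its opening sentence. It names seven events, general genital symptoms and allergic reactions, and it already covers three of the five LV-003 terms. Nausea and painful urination are asked about at every visit (5.1). The LV-003 difference is descriptive, with no test, interval or arm counts. It came from a capsule of 5 × 10⁸ CFU, below either dose this protocol states, in women with recurrent bacterial vaginosis. The 355-woman trial of the predecessor product found events equally distributed except for discharge. In UW/LB-001, done in women with recurrent UTI, neither nausea nor dysuria is listed among the commonest effects.

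All of this stands, and it limits how strongly the two terms should be worded. It does not justify leaving them out, because section 11 itself relies on descriptive capsule data from LV-001.

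Several stronger readings are tempting but are not supported:

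- *Women have been under-informed.* The consent pages were not available, and 11.1.1 does not say that only the risks it lists will be explained.
- *Clinicians are not told.* The LV-003 paragraph is in this protocol and says it plainly.
- *A number of extra cases can be projected for this trial.* That would carry a descriptive threshold over to a different dose, delivery form and population.
- *LV-001 yields a rate of severe related events for the product.* The background reads "Three subjects each experienced a single severe, treatment-related AE: abdominal pain, vaginal candidiasis, vaginal burning sensation, vaginal hemorrhage and vaginal irritation". No arm is given, and related in that study means related to either LACTIN-V or the control capsule. All but vaginal hemorrhage are already covered in 11.1.1 by name or by the general phrase.
- *A participant will miss a smear that is due.* This is possible but speculative.

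**Conclusion.** The point holds, and it is minor. Section 11.1.1 is contradicted by the protocol's own record: risks are not wholly unknown, and two of the five events reported more often on LACTIN-V in LV-003 are missing. Sections 11.1.2 and 11.1.4 state a benefit that appears in none of the seven scheduled visits.

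The conclusion on risk assumes that section 11 is meant to summarize known product effects, as its use of LV-001 suggests. It makes no claim that LACTIN-V causes nausea or dysuria. Dysuria's place in the UTI definitions makes disclosure more relevant; the documents give no basis for inferring a biased efficacy comparison from it.

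The count in the LV-001 sentence (three women with one event each, yet five events named) is a separate editorial slip.

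**What to change.** - **11.1.1:** replace the opening statement with the observed record. Add nausea and dysuria from LV-003, and say that the difference was descriptive and came from the lower-dose capsule. Add that LV-006 reported adverse events, and LV-005 genitourinary events, as evenly distributed between arms.
- **Consent form:** check that it matches the revised 11.1.1.
- **11.1.2 and 11.1.4:** delete the Pap smear statements, or reconcile them with the visit lists, laboratory sections and flow chart.
- **2.2.2.2, LV-001:** check the number of severe related events against source and correct the sentence.

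The cost is text edits, any matching change to the consent form, and notification of the IRB. No procedure is added if the Pap smear statements are deleted, and no analysis changes.
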